6.3. Analysis Populations

6.3.1. Safety Population

The Safety Analysis population includes all subjects who received at least one study vaccination.

6.3.2. Modified Intention-to-Treat (mITT) Population

The modified intent-to-treat (mITT) population includes all subjects who received at least one study vaccination and contributed both pre- and at least one post-study vaccination venous blood samples for immunogenicity testing (HAI or Neut antibody assays) for which valid results were reported. For analyses using the mITT population, subjects will be grouped based on randomized study arm.

6.3.3. Per-Protocol Population

The Per-Protocol (PP) population includes all subjects in the mITT subset with the following exclusions:

- Data from all available visits for subjects found to be ineligible at baseline.
- Data from all visits subsequent to major protocol deviations, such as:
 - Second study vaccination not received,
 - Second study vaccination received out of window,
 - Receipt of non-study licensed live vaccine within 30 days before or after each study vaccination,
 - Receipt of non-study licensed inactivated vaccine within 14 days before or after each study vaccination,
 - Receipt of immunosuppressive therapy (e.g., corticosteroids) within 30 days before or after each study vaccination.
- Data **from** any visit that occurs out of window:
 - Visit 3 data collected before 6 days or after 10 days post first study vaccination
 - Visit 4 data collected before 20 days or after 29 days post first study vaccination.
 - Visit 6 data collected before 6 days or after 10 days post second study vaccination.
 - For subjects who did not receive the second study vaccination, visit 6 data collected before 27 days or after 31 days post first study vaccination.
 - Visit 7 data collected before 20 days or after 29 days post second study vaccination.
 - For subjects who did not receive the second study vaccination, visit 7 data collected before 41 days or after 50 days post first study vaccination.

- Visit 10 data collected before 165 days or after 195 days post second study vaccination.
- For subjects who did not receive the second study vaccination, visit 10 data collected before 200 days or after 216 days post first study vaccination.

For analyses using the PP population, subjects will be grouped based on study vaccinations received.

6.4. Covariates and Subgroups

As a protocol defined exploratory analysis, HAI antibody response following the second vaccination will be summarized stratified by the following covariates: age (categorical: 18-34, 35-49, 50-64), sex (male, female), body mass index (<30 , ≥ 30), and prior receipt of seasonal influenza vaccine(s) (receipt of 2017-2018 or 2018-2019, or receipt of neither), and these covariates will be considered in statistical modeling as described in Section 8.3. As these analyses are exploratory the study was not powered for any subgroup analyses.

6.5. Missing Data

All attempts will be made to collect all data Per-Protocol. As missing data are expected to be minimal, no imputation will be performed for missing values. Any data point that appears to be erroneous or inexplicable based on clinical judgment will be investigated as a possible outlier. If data points are identified as outliers, sensitivity analyses will be performed to examine the impact of including or excluding the outliers. Any substantive differences in these analyses will be reported.

6.6. Interim Analyses and Data Monitoring

Interim analyses will only be used to terminate this trial in the event that unanticipated safety events deemed to be of sufficient concern require such action by the sponsor. These assessments will not be made on the basis of testing a formal statistical hypothesis; therefore, p-value adjustment will not be made to any analyses. A DSMB will be convened by DMID to review study progress and participant, clinical, safety, and reactogenicity and immunogenicity data.

Clinical, safety, and reactogenicity data through approximately 180 days after the second study vaccination will represent the primary clinical database for this trial. Once the last subject completes the visit that occurs approximately 180 days after second study vaccination and all HAI and Neut results are received, a “topline” subset of the immunogenicity and safety tables will be provided to DMID on an expedited timeline. These analyses may be made available to the sponsor for planning subsequent trials and to the lead PI for publication and will be considered the final analysis of these data.

Emergent public health needs may dictate additional interim safety, reactogenicity, and/or immunogenicity analyses be performed on available information at any time during the trial. If this occurs, immunogenicity data will be analyzed as results are available from the central immunogenicity laboratory.

6.6.1. Interim Safety Review

An interim safety review may include enrollment and demographic information, medical history, concomitant medications, physical assessments, clinical laboratory values, dosing compliance, and solicited and unsolicited AE/SAEs. Additional data may be requested by the DSMB, and interim statistical reports may be generated as deemed necessary and appropriate by DMID. The DSMB may receive data in aggregate and presented by study arm. The DSMB may also be provided with expected and observed rates of the expected AEs in an unblinded fashion and may request the treatment assignment be unblinded for an individual subject if required for safety assessment. The DSMB will review grouped and unblinded data in the closed session only. The DSMB will meet and review this data at scheduled time points or ad hoc as needed during this trial as defined in the DSMB charter. As an outcome of each review/meeting, the DSMB will make a recommendation as to the advisability of proceeding with study vaccinations (as applicable), and to continue, modify, or terminate this trial. Summaries prepared for the DSMB are defined separately in a report shell reviewed and approved by the DSMB.

Additionally, this trial will be monitored to determine if any of the halting rules described in Protocol Section 9.5 are met.

6.6.2. Interim Immunogenicity Review

Clinical, safety, and reactogenicity data through approximately 180 days after the second study vaccination will represent the primary clinical database for this trial. Once the last subject completes the visit that occurs approximately 180 days after second study vaccination and all HAI and Neut results are received, a “topline” subset of the immunogenicity and safety tables will be provided to DMID on an expedited timeline. These analyses may be made available to the sponsor for planning subsequent trials and to the lead PI for publication and will be considered the final analysis of these data.

Should emergent public health needs dictate interim immunogenicity review, immune responses will be summarized in terms of strain-specific 2017 A/H7N9 HAI and Neut antibody titers. Any immunogenicity reports would be provided by the SDCC to the DMID Scientific Lead and CPM, and the DSMB. Reports would include data summarized by treatment arm.

6.7. Multicenter Studies

Although randomization was stratified by site, data will be pooled across all clinical sites for all analyses. Center effects are not anticipated because the sites are using standardized procedures for vaccination and assessment of solicited and unsolicited AEs, and the study relies on a central laboratory for immunogenicity assessments.

6.8. Multiple Comparisons/Multiplicity

This study was designed to obtain preliminary estimates of safety and immune response to the A/H7N9 vaccination in healthy adults. The study was not designed to test any specific null hypothesis, and as such no adjustment for multiple comparisons will be performed.

7. STUDY SUBJECTS

7.1. Subject Disposition

[Table 13](#) will present a summary of the reasons that subjects were screened but not enrolled.

The number and percentage of enrolled subjects excluded from each analysis population by study arm are presented in [Table 14](#). A listing of subjects excluded from each analysis population will be presented in [Listing 5](#).

The disposition of subjects in the study will be tabulated by study arm in [Table 15](#). The table will show the total number of subjects screened, randomized, receiving the first study vaccination, receiving the second study vaccination, completing the blood draw for the primary immunogenicity endpoints, and completing the last visit.

A flowchart showing the disposition of study subjects, adapted from the CONSORT Statement [4] will be included and will present the number of subjects screened, randomized, lost to follow up, and analyzed, by study arm (see [Figure 1](#)).

A listing of subjects who were discontinued from treatment or terminated from study follow-up and the reason will be included in [Listing 2](#).

7.2. Protocol Deviations

A summary of subject-specific protocol deviations will be presented by the deviation category and deviation type, study arm, and age stratum for all enrolled subjects in [Table 8](#). Major deviations that will be reviewed for possible exclusion of immunogenicity results from the PP population include deviations related to eligibility/enrollment, treatment administration schedule, follow-up visit schedule, and receipt of exclusionary vaccines or medications. All subject-specific protocol deviations and non subject-specific protocol deviations will be included in [Listing 3](#) and [Listing 4](#).

8. IMMUNOGENICITY EVALUATION

Analysis of all immune responses will be conducted using the PP population. In addition, primary endpoint analyses will be conducted with the mITT population. Immune responses in terms of strain-specific A/H7N9 HAI and Neut antibody titers will be summarized by study arm at each time point. Descriptive summary statistics will be provided for all assays and time points including number of subjects with non-missing results, percentage of subjects with titers $\geq 1:40$, percentage of subjects achieving seroconversion, and GMTs along with corresponding 95% CI. Exact confidence intervals will be presented for proportional endpoints. Summaries of primary and secondary immunogenicity endpoints are presented in [Table 23](#), [Table 24](#), [Table 25](#), and [Table 26](#).

Reverse cumulative distribution (RCD) curves will be presented for post-vaccination HAI and Neut antibody titers. Plots for each assay will be generated with 4 panels (8 days post vaccination 1, 21 days post vaccination 1, 8 days post vaccination 2, 21 days post vaccination 2, and 180 days post vaccination 2), and separate curves within each panel for each study arm, as shown in [Figure 2](#), [Figure 3](#), [Figure 4](#), and [Figure 5](#).

Figures depicting the HAI and Neut GMT over time will also be presented as shown in [Figure 6](#), [Figure 7](#), [Figure 8](#), and [Figure 9](#).

The spearman correlation between HAI and Neut antibody titers will be calculated at each time point over all groups. The correlation will be depicted in scatter plots as [Figure 10](#) and [Figure 11](#).

Individual HAI and Neut assay results will be provided in [Listing 8](#) and [Listing 9](#).

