10.3 Treatment Assignment Procedures

10.3.1 Randomization Procedures

Per ICH guideline E6: Good Clinical Practice (GCP), screening records will be kept at each participating VTEU site to document the reason why an individual was screened, but failed trial entry criteria. The reasons why individuals failed screening will be recorded in the Statistical Data Coordinating Center’s (SDCC) AdvantageEDCSM (Electronic Data Capture System).

Once consented and upon entry of demographic data and confirmation of eligibility for this trial, the subject will be enrolled, randomly assigned to 1 of 4 treatment groups. All subjects will receive 2 vaccinations; the same dose will be given to the subject at both the first and second vaccination. Subjects will be randomized with allocation 2:2:2:1 into 4 groups, stratified by site (see Table 1) and by prior receipt of at least one of the 2017-2018 and/or 2018-2019 seasonal influenza vaccines to receive IM 2017 H7N9 IIV at 3.75 mcg, 7.5 mcg or 15 mcg at Days 1 and 22 with MF59[®] adjuvant or 15 mcg at Days 1 and 22 administered without adjuvant.

Enrollment of subjects will be done online using the enrollment module of AdvantageEDCSM. The randomization code will be prepared by statisticians at the SDCC and included in the enrollment module for this trial. AdvantageEDCSM will assign each subject to a treatment arm after the demographic and eligibility data have been entered into the system. A designated individual at each participating VTEU site will be provided with a code list for emergency unblinding purposes, which will be kept in a secure place.

Instructions for use of the enrollment module are included in the AdvantageEDCSM User’s Guide. Manual back-up procedures and instructions are provided for use in the event that a participating VTEU site temporarily loses access to the Internet or the online enrollment system is unavailable.

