10.5.3 Immunogenicity Data

Summaries and analysis of immunogenicity data will be presented for the mITT and PP populations.

Immune responses in terms of strain-specific 2017 H7N9 HAI and Neut antibody titers will be summarized by treatment arm at each time point. Analyses will include percentage of subjects with a titer ≥ 40 , percentage of subjects achieving seroconversion (defined as either a pre-vaccination titer < 10 and a post-vaccination titer ≥ 40 or a pre-vaccination titer ≥ 10 and a minimum four-fold rise in post-vaccination antibody titer), and GMTs along with corresponding 95% confidence intervals. Descriptive summary statistics will be provided for all assays and time points. The correlation between HAI and Neut antibody titers will be evaluated. Plots such as reverse cumulative distributions or longitudinal presentations of GMTs will be presented.

Additionally, the immune response, as described above, will be summarized by available covariates, such as age, sex, body mass index, and prior receipt of seasonal influenza vaccine(s), and these covariates may be considered statistical modeling. As an exploratory analysis, models will be developed to evaluate the relationship between dosage and adjuvant on immune response. For example, logistic regression may be used to examine the relationship of proportion of responders with dosage and adjuvant, and available covariates may be considered for inclusion in the model.

Additionally, N9 NA specific antibody assays are in development. N9 NA specific responses

may be assessed at baseline, and 8, 22, 29, 43 and 202 after receipt of the first study vaccination. For each time point summaries will include percentage of subjects with detectable N9 NA response (to be defined in SAP following assay development and selection) and GMTs along with corresponding 95% confidence intervals. Descriptive summary statistics will be provided for all assays and time points. The correlation of N9 NA response with HAI and Neut antibody titers will be evaluated, and plots such as reverse cumulative distributions or longitudinal presentations of GMTs will be presented.

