5. SAMPLE SIZE CONSIDERATIONS

This study is planned to enroll 106 subjects in each adjuvanted study arm and 53 subjects in the unadjuvanted study arm. Randomization at each site will be stratified by prior receipt of season influenza vaccines, however there is no enrollment target for these strata. The sample size for this study was selected to obtain preliminary estimates in a time critical manner. While this study is not designed to test any specific null hypothesis, the following tables illustrate the precision and power that is available for select estimates and comparisons of interest.

[Table 4](#) indicates the probability of observing one or more safety events, such as solicited injection site or systemic reactogenicity events or an unsolicited non-serious AE of a particular type for a single study arm (N = 53, 106) and for all subjects receiving adjuvanted vaccine (N = 318).

Binomial confidence intervals (CI) are widest (have the least precision) when the response rate is 50%. [Table 5](#) is presented to indicate the worst-case scenario for precision of observed exact (Clopper-Pearson) binomial confidence intervals.

[Table 6](#) illustrates the minimum detectable differences in the proportion of subjects responding (e.g., attaining seroconversion or a titer $\geq 1:40$) between two adjuvanted study arms within each stratum using a two-sided Likelihood Ratio Test and $\alpha = 0.05$.

Power calculations assume $n=100$ per adjuvanted group and $n=50$ for the unadjuvanted group. Based on previous DMID A/H7N9 trials it is expected 5% of enrolled subjects in this stratum may be excluded from analysis of the primary endpoint. In the event that only 100 subjects are actually enrolled in a study arm, the small dropout rates anticipated would have a minimal impact on the calculations presented in [Table 7](#).

Per FDA guidance [5,6], for differences in HAI antibody response rates, the lower confidence limit on the appropriate point estimate excluding equality (i.e., 0 for the difference parameter) may be sufficient to demonstrate the added value of the adjuvant. [Table 7](#) shows the lower bound of the 95% confidence interval for the difference in the proportion of responders between the adjuvanted and unadjuvanted arms (e.g. 15 mcg + MF59 minus 15 mcg unadjuvanted) assuming the proportion of responders in the unadjuvanted arm is 0.10 and considering a range for the proportion of responders in the adjuvanted arm ranges from 0.50 to 0.90.

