9.7.1 Sample Size**Table 4: Power (%) to Detect Safety Events**

Event Frequency	N = 53	N = 106	N = 318
≥10% Very Common	>99	>99	>99
≥1% Common	41	65	95
≥0.1% Uncommon	5	10	27
≥0.01% Rare	<1	1	3

Table 5: Precisions of Binomial Confidence Intervals

N	95% CI
53	36-64
106	40-60
318	44-56

Table 6: Minimum Detectable Difference in Proportion Responders with 80% Power

Assumed Proportion of subjects with titer ≥40 in comparator arm	Minimum Detectable Difference (N = 100)
0.40	0.20
0.50	0.29
0.60	0.19
0.70	0.17
0.80	0.14
0.90	0.09

Table 7: Lower Confidence Bound for Difference in Proportion of Responders Between Adjuvanted (N = 100) and Unadjuvanted (N = 50) Arms, 18-64 Years Stratum

Adjuvanted Study Arm	Unadjuvanted Study Arm	Difference	Lower Confidence Bound^a
0.50	0.10	0.40	0.26
0.60	0.10	0.50	0.36
0.70	0.10	0.60	0.46
0.80	0.10	0.70	0.56
0.90	0.10	0.80	0.67

^a Farrington-Manning confidence limits.

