Figure 10: Correlation of Hemagglutination Inhibition Antibody and Neutralizing Antibody Against A/Hong Kong/125/2017 (H7N9) by Study Day and Study Arm - Modified Intent-to-Treat Population

[Implementation Note: A generic sample figure is shown below. The scatter plots should be presented in a single figure with separate panels for each visit (Baseline, D8, D22, D29, D43, D202. Visit labels should be included in the panel header. Within each panel distinct marker types and colors should be used to indicate the study arms, with treatment group labels included in a legend.). Each study arm should have a unique color and marker shape. The spearman correlation should be calculated over all subjects and annotated within each panel as “Spearman Correlation ($r=0.xx$, $p=0.xx$)”.]

[figure not shown]

Figure with Similar format:

Figure 11: Correlation of Hemagglutination Inhibition Antibody and Neutralizing Antibody Against A/Hong Kong/125/2017 (H7N9) by Study Day and Study Arm - Per-Protocol Population

Figure 12: Reverse Cumulative Distribution of Hemagglutination Inhibition Antibody against A/Shanghai/2/2013 (H7N9) by Study Day and Study Arm - Per-Protocol Population

[Implementation Note: A generic sample figure is shown below. The RCD curves should be presented in a single figure with separate panels for each study day (Baseline[Day1], Day 8, Day 22, Day 29, Day 43, Day 202. Visit labels should be included in the panel headers. Within each panel individual curves should be used for each study arm (four curves). Each study arm should have a separate color.]

[Implementation Note: repeat for all heterologous strains]

[figure not shown]

Figure with Similar Format:

Figure 13: Reverse Cumulative Distribution of Hemagglutination Inhibition Antibody against A/Guangdong/17SF003/2016 (H7N9) by Study Day and Study Arm - Per-Protocol Population

[figure not shown]
Figure 14: Reverse Cumulative Distribution of Neutralizing Antibody against A/Shanghai/2/2013 (H7N9) by Study Day and Study Arm - Per-Protocol Population

Figure 15: Reverse Cumulative Distribution of Neutralizing Antibody against A/Guangdong/17SF003/2016 (H7N9) by Study Day and Study Arm - Per-Protocol Population

Figure 16: Geometric Mean Titers of Hemagglutination Inhibition Antibody against A/Shanghai/2/2013 (H7N9) by Study Day and Study Arm - Per-Protocol Population

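### The Spearman correlations are pooled over arms planned to respond differently, so after vaccination r and p can mix the treatment effect with subject-level association

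*SAP*

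**What the plan says.** Protocol 10.5.3 is brief on the two assays: "The correlation between HAI and Neut antibody titers will be evaluated". SAP section 8 fixes the method and level: "The spearman correlation between HAI and Neut antibody titers will be calculated at each time point over all groups". The implementation note to Figure 10 agrees: "The spearman correlation should be calculated over all subjects and annotated within each panel", with both r and a p-value in the annotation. The note to Figure 20 repeats the rule for the drifted strains, and Figures 21 to 25 follow its format. Figures 20-21 plot HAI against Neut for each drifted strain. Figures 22-25 plot vaccine-strain titers against drifted-strain titers.

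The arms are shown separately in the plots: "Within each panel distinct marker types and colors should be used to indicate the study arms". The figure titles also say that the correlation is by study day and study arm. The coefficient itself is not by arm, and no within-arm or arm-adjusted value appears in either document.

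The design expects large differences between arms. The sample-size section of the SAP works "assuming the proportion of responders in the unadjuvanted arm is 0.10" and considers a "range for the proportion of responders in the adjuvanted arm ranges from 0.50 to 0.90". Protocol 10.3.1 gives the allocation: "Subjects will be randomized with allocation 2:2:2:1 into 4 groups". SAP section 8.3.1 expects almost no antibody in any arm at baseline.

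**The concern.** When two measurements both rise with treatment, pooling treated and untreated subjects produces a positive rank correlation even if, within every arm, a subject's HAI titer says nothing about that subject's Neut titer. The coefficient is then partly a restatement of the adjuvant effect, which the plan already reports through GMTs, response rates and regression models by arm.

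The heterologous-strain figures are where this matters most. Cross-reactivity is an exploratory objective. Protocol 10.5.3 lists correlation with the vaccine-strain response and association with dose and adjuvant as separate summaries, and a pooled coefficient combines them. SAP 8.3.3 plans no formal testing for these strains, yet the shell prints a p-value that can be small because of the arm difference alone. Between-arm spread also changes from Day 1 to Day 43 to Day 202, so pooled values are not comparable across panels.

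**Working it through.** **Inputs from the documents.** Planned evaluable numbers are 100/100/100/50 (SAP Table 7: "Between Adjuvanted (N = 100) and Unadjuvanted (N = 50) Arms, 18-64 Years Stratum"). Response rates, taken as P(titer ≥ 40), are 0.10 unadjuvanted and 0.50 to 0.90 adjuvanted. Titers lie on the grid 10·2^k, and values below 10 are set to 5 (SAP 4.5.2).

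**Inputs assumed.** The within-arm latent correlation of log2 titers is set at 0, 0.3, 0.5, 0.7 or 0.9, and the within-arm SD at 1.0, 1.5 or 2.5 log2 units. The planning rates are introduced for HAI response. Applying them to Neut or to drifted strains is a further assumption.

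**The plan's own figures.** Neither document gives a value or target for this correlation, so there is none to reproduce. The planning rates can be checked through SAP Table 7. Farrington-Manning lower limits come out at 0.256, 0.356, 0.458, 0.563 and 0.672, against the printed 0.26, 0.36, 0.46, 0.56 and 0.67.

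**Model.** Each subject has a bivariate normal pair of log2 titers, rounded down to the grid. The mean in arm a is

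μ_a = log2(40) + SD × Φ⁻¹(p_a).

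At SD 1.5 this gives 5.32 − 1.5 × 1.28 = 3.40 for p = 0.10, 5.32 for p = 0.50, and 5.32 + 1.92 = 7.24 for p = 0.90. There were 250 replicates per setting.

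**Results at SD 1.5, both assays shifting equally (mean Spearman, pooled vs within arm).**

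| Latent correlation | Adjuvanted 0.50 | Adjuvanted 0.90 | Dose gradient 0.5/0.7/0.9 |
|---|---|---|---|
| 0 | 0.14 vs 0.00 | 0.32 vs 0.00 | 0.38 vs 0.00 |
| 0.3 | 0.38 vs 0.27 | 0.51 vs 0.28 | 0.55 vs 0.27 |
| 0.5 | 0.54 vs 0.46 | 0.64 vs 0.46 | 0.67 vs 0.46 |
| 0.7 | 0.70 vs 0.65 | 0.77 vs 0.65 | 0.79 vs 0.65 |
| 0.9 | 0.88 vs 0.85 | 0.90 vs 0.85 | 0.91 vs 0.85 |

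The excess is therefore 0.14 to 0.38 at latent correlation 0. At 0.5 it is 0.54 − 0.46 = 0.08 up to 0.67 − 0.46 = 0.21. At 0.9 it is 0.88 − 0.85 = 0.03 up to 0.91 − 0.85 = 0.06. Results at SD 1.0 and 2.5 are similar.

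**The printed p-value.** With zero within-arm association and SD 1.5, pooled p < 0.05 occurs in about 74% of simulated trials at 0.50 adjuvanted response. It occurs in 100% at 0.90 and under the dose gradient.

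**Where the effect vanishes or reverses.** With response 0.01 in every arm, a stand-in for Day 1, pooled and within-arm values coincide (0.29 vs 0.29 at latent correlation 0.5, SD 1.5). If HAI differs between arms while Neut response is 0.70 in all of them, pooling lowers the coefficient: 0.40 vs 0.46 at latent correlation 0.5, and 0.73 vs 0.85 at 0.9.

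**The remedy.** Ranking all subjects and adjusting the ranks for arm gives a correlation within about 0.01 of the within-arm value at SD 1.5, and within about 0.03 at SD 2.5.

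**The case against.** The best defence is that a pooled correlation is a legitimate description of how two titers move together over the full range that the trial produces. The plots mark the arms, so a reader can see clustering, and Listings 8-9 give individual titers with study arm. The coefficient is not an endpoint and no decision depends on it. All of this stands, and it limits the weight of the point. It does not change what the printed r and p contain, and those are the numbers that will be quoted.

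Within-arm coefficients have weaknesses of their own. The share of the unadjuvanted arm tied at 5 is Φ(1.2816 − 2/SD): 24%, 48% and 68% at SD 1.0, 1.5 and 2.5. With n = 50 and r = 0.45, the approximate 95% interval is tanh(atanh 0.45 ± 1.96/√47), or 0.20 to 0.65. This is a good reason to add to the pooled value and not to replace it.

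A reader might also infer two stronger claims that the documents do not support:

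- **That the plan fails to measure agreement between the assays.** Neither document claims to measure agreement, concordance or interchangeability. Nor would pooling be the cause: a constant offset between assays leaves Spearman unchanged within a single arm (0.91 before and after).
- **That pooling always inflates the coefficient.** The working shows no effect without arm differences, little when within-arm correlation is already high, and a reduction when only one assay responds. The documents give no Neut or drifted-strain rates by arm that would settle the direction.

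**Conclusion.** The point holds, at low severity. The plan specifies one pooled r and p per visit and nothing that separates subject-level association from the arm effect. If both titers shift with arm at the planning rates, the post-dose-2 coefficient is too high as a measure of within-arm association. The excess is large if the assays are unrelated within arm, moderate at latent correlation 0.5, and slight at 0.9. The pooled p-value is not evidence of association within arms, since it is usually below 0.05 when there is none.

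These sizes rest on an assumed within-arm correlation and SD, and on applying HAI planning rates to the second titer. The actual size, and even the sign, will depend on the data. The analysis is descriptive, and the primary and secondary results are unaffected.

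**What to change.** In SAP section 8 and the notes to Figures 10-11 and 20-25:

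- Add an arm-stratified (partial) Spearman over all subjects, and name it as the value for subject-level association between assays or strains.
- Add the four within-arm Spearman coefficients with confidence intervals.
- Keep the pooled r, labelled as including differences between arms, and do not use its p-value as evidence that the assays or strains are associated.
- Apply the same rule in the NA addendum promised in SAP 8.3.4, since Protocol 10.5.3 also plans correlations of the N9 NA response with HAI and Neut.

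The cost is a few more numbers per figure. No new data are needed. The estimate for the 50-subject unadjuvanted arm will be imprecise and heavily tied, and should be footnoted as such.
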